7.2 Sample size

LSGG are presently being performed in a small minority of hospitals in Norway, but the technique used differs between hospitals and surgeons making the results difficult to interpret. However, in order to avoid a potential influence from these hospitals on the power calculations, these hospitals have been excluded from this sample size evaluation.

The sample size calculation is based on stipulated changes in the use of ARM since we gather this as the most relevant known clinical variable reflecting patients symptoms.

According to recent, unpublished data from SOReg-S and SOReg-N, we find a three-fold increase in the use of ARM from preoperatively until two years after LSG for both countries. The prevalence of ARM-use before LSG however differs between the countries: In Norway, approximately 7% of the patients are using ARM on a daily basis while the corresponding figure in Sweden is approximately 5%.

In Norway, the use of ARM increase from 7 % to approximately 20 % as a mean observed at the two-year follow-up, while in Sweden the corresponding numbers are 5 % increasing to approximately 13%.

Since the population and number of hospitals performing bariatric surgery in Sweden is about twice that of Norway, we estimate a 2:1 composition of participants. Hence, the composite figures will be ≈ 6 % at baseline, increasing to ≈ 16 % at two years.

In order to account for a potential improvement in the LSG-group because of participation in a study (the Hawthorn-effect), the estimated rate for ARM-use in the LSG-group at two years will be set at 14 %.

	RESEARCH PROTOCOL
Version no 4.0	Clinical intervention study

According to the clinical experience encountered by [name] et al, adding gastropexy to the LSG reduced a rise in the use of PPI from preoperatively until two years. Stipulating a change from 6 to 14% in the LSG group, and from 6 to 7% in the LSGG-group, this will require a total of 686 patients using power 1 - beta = 85%.

7.3 The level of significance and power of the clinical study

We have used the significance level of alpha = 5 % and power 1 - beta = 85 %.

7.4 Expected drop out rates

Based on clinical experience we estimate a drop out rate of \approx 20% at two years. Adding this to the equation will make it necessary to randomize 858 patients. To be on the conservative side we plan to randomize 900 patients.

7.5 Pass/fail criteria

Using ARM or having been reoperated due to GORD will be classified as a failure for the main outcome.

7.6 Provision for interim analyses

Interim analysis will be performed for complications by the DMC. Complications will be evaluated and compared between the two groups based on 30 day morbidity rates by data extraction and analysis every sixth month.

7.7 Criteria for stopping the clinical study

Major complications possibly related to the surgical technique will be looked into and evaluated in detail.

Significantly more complications in one of the groups will be discussed in the TSC and if needed, necessary actions will be taken if needed.

7.8 Specification of subgroups

Gastroscopy and pH-metry of the distal oesophagus will be performed in a subgroup of 30 patients in hospitals where the Bravo capsule is available. Patients suspected of having non-acid reflux will be recommended pH- impedance measurements.

Patients having been reoperated due to reflux will be classified as failures and analyzed together with the ARM-group in their original cohort (LSG or LSGG), according to the ITT-principle.

Patients having been reoperated for other reasons (rare) will also be included in the ITT analysis.

7.9 Procedures to take into account all subject data

Patients reoperated due to reflux will be grouped together with patients in the same group as those using ARM, thereby making ITT analysis possible for both main outcomes.

7.10 Treatment of missing, unused, spurious data

Missing data for outcome will be handled by multiple imputation. For main outcome and PRO at two years this will be based on baseline and one-year data, while for the secondary outcome of endoscopic (and pH metry) findings this will be based mainly on baseline data.

	RESEARCH PROTOCOL
Version no 4.0	Clinical intervention study

Similarly, missing data for five years will be handled by multiple imputation including two-year data.

Continuous variables will also be analysed by mixed effect models that can handle missing values.

Patients with missing baseline data will be excluded from the study.

Since every patient will be assigned a unique identifying number it will be possible to double-check any spurious data against the patients medical record. Spurious data discovered within a participating hospital will be double-checked against the patients medical record before transferring to the common study database in Norway. For spurious data discovered after transfer to the common database, the project leader will contact the national coordinator or the participating hospital querying the data.

7.11 Exclusion of data from hypothesis testing

Patients will be excluded for main outcome (hypothesis testing) if baseline data is missing.

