4 PROJECT METHODOLOGY

Hospitals performing more than 10 LSG annually will be invited to participate. A maximum of 200 patients will be accepted from any hospital. The start of the study is the date at which the first patient is operated. The inclusion of new patients will stop when 900 patients have been included (i.e. randomized), estimated to be reached after approximately two years. The number of included patients will be monitored continuously.

Evaluation of outcome will be based on data at two and five years postoperatively. Given an inclusion period of maximum two years, follow-up after two and five years, and another year for delayed follow-up and data processing, the project period will be for a maximum of eight years.

This study is an international, multicentre, randomized, triple-blind (blinded to patients, caregivers and researchers) prospective clinical intervention trial. For primary and secondary endpoints, analysis will be performed according to ITT. All patients will thus be analysed within the allocated group.

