5.1.6 Including more subjects to compensate for drop-outs

If the recruitment of patients are lower than expected in Norway and Sweden, hospitals in other countries (primarily Netherland) will be invited to participate.

In order to reduce drop-outs, patients will be randomized in the operating room after being anesthetized and after the surgeon has decided to proceed with a LSG, but before surgery starts. Randomization will be performed by the use of sealed envelopes containing information on group allocation. Any patient who has signed for participation but are withdrawn before randomization will be replaced by one new subject. A list of patient(s) who withdraw after inclusion must be kept at the participating hospital and the reason for withdrawal must be stated. This list should be presented to SOReg-N on the first day of every month (see also 6.6.2).

Patients who withdraw or are withdrawn from the study after randomization cannot be replaced.

	RESEARCH PROTOCOL
Version no 4.0	Clinical intervention study

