Each participating hospital will point out one person to coordinate the study within that hospital. This includes patient recruitment, obtaining written informed consent, local data management, correspondence with the national coordinator and with the Project Leader / institution responsible for this study. All included patients will be given a unique patient ID number. This number is the ID that is generated automatically by SOReg. All included patients in Sweden will thus have a six digits code number and all included patients in Norway will have a five digits code number. An updated list of included patients with overview of group allocation must be kept in a safe place within the hospital. A copy of this list containing the patient ID (no name or other identifiable data) shall be sent to SOReg-N on the first day of every month (see also 5.1.5 and 5.1.6 and appendix 17.6). Hospitals participating in the Bravo-arm of the study must balance the number of patients themselves so that an equal number of patients are allocated to the pexy and no-pexy group, respectively.

6.6.3 Factors that may compromise the outcome of the clinical study / interpretation of the results

This study is a randomized trial where the patients will be randomized into two groups. Potential differences between the groups like age, preoperative use of ARM and smoking will be accounted for by statistical methods.

Potential differences in performance between surgeons will be explored and adjusted for by statistical methods if found.

Missing values at two years will be accounted for by multiple imputation as necessary. Missing value at baseline will exclude the patient from the study.

Potential differences in culture and tradition between hospitals and countries for prescribing ARM, and similarly potential differences among patients demand for having ARM will be sought overcome by standardizing the information: ARM used in conjunction with the operation should be stopped at the latest by four weeks postoperatively. Patients using ARM after this period should actively be asked about this at the first follow-up (usually six weeks), and if no obvious reason exists it should be stopped. Similarly, if a patient is using ARM at the one-, two- or five year follow-up, the reason for this should be addressed.

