7 STATISTICAL CONSIDERATIONS

7.1 Statistical design

Patients will be allocated in a 1:1 fashion between LSG and LSGG. Participating hospitals will administer this by block randomization with 10 patients (i.e. 5 LSG, 5 LSGG) in each block. Group allocation will be determined by opening of sealed envelopes. The envelopes will be distributed to participating hospitals from SOReg-N.

All patients will be given a unique patient number, and SOReg-N will be informed regularly about group allocation.

Analysis for outcome will be performed according to ITT. All patients will thus be analysed within the allocated group. Missing data at two and five years will be handled by multiple imputation. The main analysis for outcome will be based on logistic mixed effect models with odds ratio between groups corrected for age, smoking and surgeon. A sensitivity analysis including hospitals will also be performed.

Information on group allocation will be blinded to patients and researchers.

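### Patients with missing baseline data are excluded from the primary test, so the primary analysis as written is not the ITT analysis of all randomized patients that the protocol promises

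*Protocol*

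**What the plan says.** Two sets of statements govern who enters the primary analysis.

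**All patients are kept.** Section 4: "For primary and secondary endpoints, analysis will be performed according to ITT. All patients will thus be analysed within the allocated group". Section 7.1 repeats it: "Analysis for outcome will be performed according to ITT. All patients will thus be analysed within the allocated group".

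**Patients with missing baseline data are removed.** Section 6.6.3: "Missing value at baseline will exclude the patient from the study". Section 7.10: "Patients with missing baseline data will be excluded from the study". Section 7.11, on exclusions from hypothesis testing: "Patients will be excluded for main outcome (hypothesis testing) if baseline data is missing".

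Four other places bear on how these fit together:

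- Section 4 treats included and randomized as the same thing, with a target of 900.
- Section 5.1.6: "Patients who withdraw or are withdrawn from the study after randomization cannot be replaced".
- Section 6.5.2 lists the exclusion criteria; missing baseline data is not among them.
- Sections 7.1 and 7.10 plan multiple imputation for missing outcomes. Neither plans it for missing baseline values.

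**The concern.** An analysis cannot both keep every randomized patient and drop those with a gap at baseline. As the text stands, the primary result would be reported as ITT when it is not.

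The trigger is also wide. Section 6.6.3 speaks of a missing value at baseline without limit. Under Section 6.6.1, baseline collection covers history, physical examination, laboratory tests, the patient-reported questionnaires and GerdQ. The primary model in Section 7.1 adjusts only for age, smoking and surgeon. Read literally, one absent laboratory value or unanswered questionnaire removes a patient whose medication use and reoperation status at two years are known. Section 6.5.3 pulls the other way, because it lets a patient leave the patient-reported part and remain in the rest of the study.

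At stake are the validity of the ITT label, the loss of observed primary outcomes that cannot be made up by replacement, and an exclusion decision with no stated time at which it must be made.

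**Working it through.** **1. Can the statements be reconciled?** The natural attempt is to read the exclusion as a screening rule applied before randomization. That could fit Sections 6.6.3 and 7.10 taken alone. It does not fit Section 7.11, which is an exclusion from the hypothesis test and so applies to patients already in the trial. Nor does it fit Section 6.5.2, which omits the rule, or Sections 5.1.6 and 7.1, which describe opening the envelope without any check of baseline completeness. The contradiction remains.

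**2. The plan's own sample size.** Inputs: 14% (LSG) and 7% (LSGG) at two years from Section 7.2; alpha 5% and power 85% from Section 7.3; 1:1 allocation from Section 7.1; 20% drop-out and 900 randomized from Section 7.4. The protocol does not state sidedness; two-sided reproduces its figure.

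Pooled-variance formula, with mean rate (0.14 + 0.07)/2 = 0.105:

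n per arm = [1.960 × √(2 × 0.105 × 0.895) + 1.036 × √(0.14 × 0.86 + 0.07 × 0.93)]² / 0.07²

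= [1.960 × 0.4335 + 1.036 × 0.4307]² / 0.0049 ≈ 342.8, rounded up to 343.

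Total 2 × 343 = 686, as stated. With drop-out, 686 / 0.80 = 857.5, rounded up to 858, as stated. The sample size is not in error.

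**3. Reserve for baseline exclusions.** The 20% covers drop-out at two years only. The remaining margin is 900 − 858 = 42 patients, or 42/900 = 4.7%. Equivalently, 1 − 686/(900 × 0.80) = 4.7%.

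**4. Power under the exclusion rule.** Evaluable N = 900 × (1 − m) × 0.80, where m is the share of randomized patients with missing baseline data. The protocol gives no value for m, so those below are assumptions; drop-out is taken to be the same among patients with and without complete baseline data.

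Power = Φ[(0.07 × √n − 1.960 × 0.4335) / 0.4307], with n per arm = N/2.

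| m (assumed) | Evaluable N | Power |
|---|---|---|
| 0% | 720 | 86.7% |
| 2% | 706 | 86.0% |
| 5% | 684 | 84.9% |
| 10% | 648 | 83.0% |
| 15% | 612 | 80.8% |

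These figures count every drop-out as lost. Section 7.10 plans to impute missing two-year outcomes. If imputation recovered the full information of all 900, power with no baseline exclusions would be 93.0%; that is an upper bound, not an expectation.

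**5. Who could influence the exclusion?** Under Section 5.1.5 the hospital coordinator keeps the list showing who received a pexy. Under Section 6.6.2 the same person is responsible for local data management. No section fixes when baseline completeness is judged.

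**The case against.** The strongest reply has three parts.

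*No bias is shown.* Baseline data are collected before the operation (Sections 5.1.4 and 6.6.1), and the envelope is opened only once the patient is anaesthetised (Section 5.1.6). Allocation cannot cause a gap in data already collected. If missingness is settled by then, exclusions should balance between arms and cost mainly precision and generalisability. This stands. A reader might infer that baseline data are entered or cleaned after surgery with allocation known. The protocol does not say so: it describes manual entry and review before transfer without giving a time. The operation note hides allocation, pexy status is kept out of SOReg, and investigators are blinded. What survives is narrower: one role combines knowledge of allocation with local data management, and no deadline closes the question.

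*No material power problem is shown.* A reader might infer that the trial becomes underpowered. At an assumed 5% the shortfall is two patients (684 against 686) and about 0.1 percentage points of power, before any gain from imputing outcomes. This also stands.

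*Which baseline variables count is a matter for the SAP.* This is partly right. A SAP may define the variables, and Section 6.5.3 makes the most literal reading awkward. But a SAP could not reconcile an all-patients analysis with an exclusion from the primary test without overriding one of them. The conflict is in the protocol.

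**Conclusion.** The concern holds as a contradiction in the definition of the primary analysis set. Sections 6.6.3, 7.10 and 7.11 cannot be followed together with Sections 4 and 7.1, and as written the primary analysis is not ITT. It can discard randomized, irreplaceable patients with a known two-year outcome.

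The consequence is moderate. Power stays between about 83% and 86% for assumed missing-baseline rates of 2% to 10%, against 86.7% with none, and the loss matters only if missing baseline data are common. These figures rest on the protocol's 14% and 7%, its 20% drop-out, and rates of missing baseline data that it does not supply. Selective exclusion after allocation is left possible by the text; the documents do not show that it would occur, and the point should not be read as a finding of bias.

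**What to change.** Replace the exclusion sentences in Sections 6.6.3, 7.10 and 7.11 with wording such as: *All randomized patients are included in the primary analysis in their allocated group; missing values of baseline covariates used in the model (for example smoking) are imputed.* Sections 4 and 7.1 can then stand.

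Name the covariates when doing this. Section 6.6.3 lists preoperative use of acid-reducing medication among the differences to be accounted for, but the model in Section 7.1 does not include it, so the imputation needs one agreed list.

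Cost: a protocol amendment, which under Section 9 needs steering committee agreement and ethics approval, and a small extension of the multiple imputation from outcomes to model covariates. Checking that the model covariates are complete before the envelope is opened would reduce the need for imputation; it is optional and would add a step at each site. The change should be made before outcomes by arm are examined.

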7.12 Min/max number of subjects per centre (multi-centre study)

The minimum number will be 10, and the maximum 200 subjects per center.

7.13 Special reasoning

Beside what is mentioned above, we do not see any special statistical reasoning pertaining to this study as per today.

8 DATA MANAGEMENT

8.1 Procedures for data review, database cleaning, and issuing and resolving queries

Each participating country will have a national coordinator who will review the captured data and query individual hospitals for odd values. Only reviewed and cleaned data will be transferred to the central database in Norway.

This study will have a TSC consisting of five members: Two from Norway (including the project leader) and three from Sweden. If more countries are included, one representative from each other country will be included. The TSC will carry the main responsibility for the study. Potential queries not intended for the DMC will be solved in the TSC.

8.2 Procedures for verification, validation and securing electronic data systems

Data will be entered manually into an approved register. In Norway and Sweden this will be SOReg. Each patient will be deidentified and given a unique number before transferring data to the central database for the project (i.e. in Norway).

8.3 Procedures for data retention

All data will be transferred to, and retained in a secure database at Helse Førde, Norway. Only the project leader and approved researcher(s) will have access to the database.

8.4 Specified retention period

The main focus will be on data from the two-year follow-up, however data from five year follow-up will also be published. The inclusion-period will be 2023 – 2024, and collecting five-year data will extend into 2030. It is stipulated that publications based on five-years data will extend through 2032.

	RESEARCH PROTOCOL
Version no 4.0	Clinical intervention study

Documentation for the clinical study will be retained for a period decided by the EC/REC, usually **five years** after the final study report/publication (Norway). Since we stipulate the last publication to be in 2032 the data will be deleted before 2038.

9 AMENDMENTS TO THE RESEARCH PROTOCOL

The Research Protocol may require to be amended during the conduct of the study. Any amendment to the Research Protocol will be agreed upon in the TSC. The amendments will be approved by the ethics committee (EC/REC).

10 DEVIATIONS FROM THE RESEARCH PROTOCOL

10.1 Statement that investigator is not allowed to deviate from the research protocol

The study will be performed in accordance with this research protocol.

10.2 Procedures for recording, reporting and analyzing protocol deviations

All research protocol deviations will be reviewed by the representative for the research responsible institution for impact on subject's participation in the clinical study. The representative for the research responsible institution will notify the project leader of deviations. All deviations will be reported to the appropriate regulatory bodies as required.

11 STATEMENTS OF COMPLIANCE

11.1 Statement of compliance with ethics principles

The study will be performed in accordance with the ethical requirements defined in the Declaration of Helsinki.¹⁹

11.2 Statement regarding ethical approval

The clinical study shall not commence until written approval/favourable opinion is given from the REC. Such approval will be obtained for each participating country separately.

11.3 Additional requirement from ethics committee

The clinical study performance will include any additional requirements requested/mandated by the EC/REC.

11.4 Statement of insurance cover

In Norway, patients are covered by "Norsk Pasientskadeerstatning". In Sweden, patients are covered by "Patientförsäkringen" (Patient Insurance)

12 INFORMED CONSENT PROCESS

12.1 General informed consent

Informed consent shall be obtained in writing from the subject prior to inclusion in the study.

The process must adhere to the ethical principles that have their origin in the Declaration of Helsinki. Prior to the beginning of the clinical study, the investigator will have EC/REC approval / favourable opinion of the written informed consent form and any other information intended to be provided to the subjects.

	RESEARCH PROTOCOL
Version no 4.0	Clinical intervention study

Authorised personnel will conduct the informed consent process of explaining the clinical study to the subject as well as providing the subject with a copy of the subject information sheet. The consent information will include all aspects of the clinical study that are relevant to the subject's decision to participate in the language in which the subject is most proficient. The language will be non-technical and easily understood.

The informant will avoid coercion, will not appear to waive the subject's legal rights in any way, will allow sufficient time for the subject to inquire about the details of the clinical study, ask any questions and make the decision to participate or not in the clinical study.

Should the subject decide to participate in the clinical study, the informed consent form will be signed and personally dated by the subject and by the authorised person who conducted the informed consent discussion. A copy of the consent form will be given to the subject. Any significant and relevant new information that arises during the course of the clinical study will be provided to the subject and their consent to continue will be sought.

